Acarbose, an FDA-approved diabetes medication, is one of the most promising anti-aging agents tested by the National Institute of Aging's Interventions Testing Program. Acarbose is a pseudotetrasaccharide of microbial origin, which lowers blood glucose primarily by inhibiting alpha-glucosidases, a group of enzymes that break down starch in the small intestine. This results in preferential absorption of carbohydrates at the lower small intestine, slowing of digestion time, and flattening of postprandial glucose and insulin excursions. Acarbose is primarily excreted in the feces, and approximately 1 % of acarbose is absorbed systemically, after undergoing fermentation. The string and st

In a recent study of genetically heterogeneous, non-diabetic mice, acarbose increased median lifespan by 22% in males and 5% in females.³ Maximum lifespan was increased by 11% and 9% in males and females, respectively, despite unchanged hemoglobin A1c

levels. Other notable effects include an increase in FGF-21, and decreases in weight, fasting IGF-1 and fasting insulin in acarbose-treated mice.³ In a follow-up study, acarbose started later in life (18 months) extended lifespan by 5% in male mice. Acarbose also improved age–related memory impairment in a separate mouse study.^{4,5} A study in diabetic rats showed that treatment with acarbose significantly altered the expression of miRNAs that target genes in the inflammatory pathways including interleukin 6 (IL-6), mitogen activated protein kinase 1 (MAPK-1) and tumor necrosis factor (TNF), primarily by acting through the MAPK pathway.⁴¹

In humans, treatment with acarbose has been shown to prevent the development of type 2 diabetes in high-risk individuals.⁶ In the STOP-NIDDM trial, acarbose also significantly decreased incident cardiovascular disease, including a decrease in myocardial infarctions.⁷ Subsequent studies, including a meta-analysis, have supported these findings,^{8,9} and a large clinical trial of acarbose for CVD prevention is currently underway in Asia.

¹⁰Treatment with acarbose is also associated with a decreased risk of colorectal cancer.¹¹ Taken together, these findings suggest that acarbose treatment may have pleotropic effects and support the need to study acarbose in human aging.

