Informed consent	x							
		Diananaa		Diamanaa				
OGTT & eligibility labs (\$)	X	Dispense study meds (treat- ment A)		Dispense study meds (treat- ment B)		Start treatme nt B		
Safety monitoring (*)			X				X	
serum for miRNA				X				X
Stored samples for biomarkers,				Х				X

4	EINSTEIN				
Albert Einstein College of Medicine					

Vital signs, height, weight	Х	X	X	X		X	X
History	х	Interim history	Interi m histor y	Interim history		Interim history	Interim history
Physical exam (**)	X	X					
Standard meal test (#)				х			X
Muscle & adipose tissue biopsy				X			X
Fecal collection				Х			X

- (\$) eligibility labs include OGTT, Cr, AST/ALT, CBC, urinanalysis
- (*) safety monitoring includes recording of AEs and labs (Cr. AST/ALT)
- (#) standard meal test includes: fasting hsCRP, IGF-1, HbA1c and adiponectin, lipid profile, serum microRNA, Fasting and every 30 minute glucose, insulin levels.
- Fasting and 2 hour samples stored for possible future use.
- (**) Physical exam can be performed during visit 1 or visit 2.

Consent Process:

For this clinical investigation we will be consenting the research participants in compliance with our local IRB policy, Department of Health and Human Services (HHS) regulations for the Protection of Human Research Subjects (45 CFR 46) and FDA regulations (21 CFR 50 & 56).

For an initial phone screening we will be using a phone consent form that contains also HIPAA language. We will ask for permission to collect personal information and if they agree to be contacted for other future studies.

During the screening visits in the Clinical Research Center (CRC), subjects will sign the current IRB-approved and stamped consent document.

Prior to the adipose and muscle biopsies (visit 4 and visit 6), the physician performing the procedures will obtain consent using a standard Montefiore procedural consent, again detailing the procedures and expected risks.

Study visits:

Screening visit (Visit 1): Following informed consent, a history, vitals, anthropometrics, and screening labs, including OGTT, will be obtained.

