Visit 2: Subjects for the study intervention who meet eligibility criteria (see below) will be invited to enroll in the study. Study medication (Treatment A: acarbose or placebo, double-blind) will be dispensed for the following 10 weeks. Since flatulence and abdominal discomfort are common with acarbose, slow titration is often needed. Subjects will be instructed to begin with 1 capsule with the first bite of one meal each day, and will be given instructions on titrating study medication as tolerated to 2 capsules with each meal (breakfast, lunch, and dinner) after 2 weeks. Subjects unable to tolerate any study med, will be withdrawn from the study. Subjects will be contacted every other week by phone to assess adherence and to adjust dosing if necessary. Physical exam will be performed in visit 1 or visit 2 by a licensed study physician to confirm no major physical limitations or illness prior to randomization.

Visit 3: Monitoring visit. This visit will be a visit to assess compliance and dose escalation. Subects who able to tolerate 2 capsules three times daily, will be provided with a higher dose capsule, and instructions to titrate to 2 (higher dose) capsules three times daily. If they are only able to tolerate 1 capsule three times daily of the lower dose, they will be given more of the lower dose capsule to take for the remainder of the treatment period. Interim history will be performed. Liver function tests will be checked. A fecal microbiome stool collection kit and instructions will be provided

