Adipose Biopsy: An adipose sample will be obtained from the periumbilical region. A small 0.5 cm cutaneous incision will be performed under local anesthesia and 2-6 grams of adipose tissue (which will vary depending on participant's adiposity) will be obtained by aspiration technique. Whole adipose tissue for analysis by rt-PCR will be immediately homogenized in Trizol (Life Technologies, Bethesda, MD) with a Tissumizer homogenizer. Subsequent mRNA extraction and analysis of gene expression (RNA seq) will be performed at Einstein's Sequencing Core Facility using multiplexed 100bp single-end sequencing on an Illumina HiSeq2500.

Remaining fresh adipose biopsy specimens will be immediately digested with collagenase type 1.

C.2.2 Sub-Aim 1: To assess the relationship between changes in gene expression with selected phenotypic variables and biomarkers, including changes in insulin sensitivity and glucose tolerance, vascular function, oxidative stress, inflammation, gut bacteria and/or serum microRNA profiles.

Detailed Methods

Screening OGTT: A 75-gram OGTT will be conducted in the morning following an overnight fast according to standard methods.

Standard Meal Test Protocol: A standard mixed meal challenge, rather than oral glucose challenge, represents a more physiologically relevant stimulus, in that it may more closely mimic metabolic changes experienced by individuals in daily life. Standard meal tests (SMT) with frequent blood sampling and application of mathematical modeling have been used to evaluate insulin sensitivity and insulin secretion, and have been reported to produce results comparable to more invasive and less physiologic tests.^{32, 33} Furthermore, the contribution of the incretin hormones to stimulated insulin secretion is captured, unlike intravenous tests. In our protocol, subjects are studied following an overnight fast and after a test meal of 110g CHO, 20g protein, 20g fat. Blood sampling is performed fasting and 30, 60, 120, and 180 minutes following the meal through an indwelling intravenous catheter and will be used to calculate glucose and insulin AUC. Subjects are

provided with a standard meal to consume at home on the night prior to the next SMT, in order to minimize metabolic variability between tests.

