Assessment of insulin sensitivity: Insulin sensitivity will be estimated from insulin and glucose levels obtained following the standard meal challenge, using a modification of the Matsuda index, which has been widely used for non-invasive assessment of insulin sensitivity and shows good correlation (r=0.73) with results obtained from euglycemic hyperinsulinemic clamp studies.³⁴

Measurement of markers of inflammation and oxidative stress: Measurement of circulating cytokines and acute phase reactants will be performed both fasting and at 2 hours postprandial. Plasma samples will be aliquoted into Eppendorff tubes and stored at -80° C. Subsequent measurements might include hormones, and inflammatory markers, including plasma leptin, TNF- α , PAI-1, IL-1 β , IL-6, VCAM, FGF-21, butyrate, alpha dicarbonyls, adiponectin and other aging biomarkers. Urine samples will be stored (in the presence of an antioxidant, such as BHA) and may be assayed for measurement of urine F2 isoprostanes.

Serum microRNA:

miRNA will be extracted from the serum samples using miRNeasy kit (Qiagen, CA) using the manufacturer's protocol. miRNA libraries will be prepared using NEBNext Multiplex Small RNA Library Prep for Illumina (New England Biolabs). Cel-miR-39 mimic will be added to each sample before extraction, for normalization and sent for miRNA sequencing at Einstein's Sequencing Core Facility using multiplexed single-end sequencing on an Illumina HiSeq2500

Fecal analysis for gut microbiome:

Stool collection and DNA extraction:

Stool samples will be collected at visits 4 and 6. 16s ribosomal DNA sequencing will be performed to assess bacterial species clustering. Participants will be provided with a DNA OMNIgene.Gut OMR200 kit (DNA Genotek, London, Canada) along with a stool collection hat, for self-collection of fecal samples, to be brought in for further treatment and analysis, at baseline visit 20f the study and after 12 weeks of study treatment on visit 4. The kits will be stored at room temperature until fecal microbial DNA extraction (within 30 days). Fecal microbial DNA will be extracted from the samples using PowerFecal DNA Isolation kit (MoBio Labs Inc) following manufacturer's protocol and eluted DNA will be divided into 1cc aliquots and frozen immediately at -80°C for further analysis. The purified DNA samples will be sent for 16s rDNA sequencing to Integrated Microbiome Resource, CGEB, Canada or at the Massachussets Institute of Technology (MIT).

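### If study drug is acting during the test meal, the only named insulin-sensitivity measure could rise from slower carbohydrate absorption alone, so a fasting index should be reported beside it

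*Combined protocol and SAP*

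**What the plan says.** Section C.2.2 names one measure: "Insulin sensitivity will be estimated from insulin and glucose levels obtained following the standard meal challenge", "using a modification of the Matsuda index". It supports the index by saying that it "shows good correlation (r=0.73) with results obtained from euglycemic hyperinsulinemic clamp studies". The modification is not described and no formula is given.

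The same section has subjects studied after an overnight fast and "after a test meal of 110g CHO, 20g protein, 20g fat". It gives the sampling as "Blood sampling is performed fasting and 30, 60, 120, and 180 minutes following the meal". The footnote to the visit schedule in C.1 gives it differently: "Fasting and every 30 minute glucose, insulin levels". Glucose and insulin AUC are also planned from this test. The OGTT is used for screening only.

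The Background (section B) lists among the drug's effects a "flattening of postprandial glucose and insulin excursions". Under Visit 2, subjects titrate to "2 capsules with each meal (breakfast, lunch, and dinner"), and C.1.4 has the drug taken as a meal begins. The meal test is done at Visit 4, when the first treatment period ends, and again at Visit 6. No section says whether a capsule is taken with the test meal.

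Section C.3.2 compares insulin sensitivity between acarbose and placebo by paired t-test or Wilcoxon test at two-sided 0.05. Sub-aim 1 relates changes in gene expression to changes in insulin sensitivity, among other variables.

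**The concern.** A meal-based index reads low post-meal glucose and insulin as good insulin sensitivity. Acarbose lowers post-meal glucose and insulin by acting in the gut. If it is acting during the test meal, the index can move in the favourable direction with no change in how muscle, fat or liver respond to insulin.

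Randomisation and blinding do not remove this. The active drug causes the effect, so it is part of the acarbose-placebo difference. The limitations in C.3.1 cover carryover, diet, activity and weight, but not this point. The cited correlation with the clamp (r = 0.73, so r² = 0.53) is not said to hold under a drug that alters absorption.

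Two uses are at stake. One is the paired test labelled insulin sensitivity. The other is the Sub-aim 1 correlations, which would relate expression in biopsies taken fasting (C.2.1) to an index that depends on what happens during a meal. The Background leaves open whether benefit comes through post-meal effects, gut microbes, gut hormones or direct tissue action. An index that mixes gut and tissue action makes that question harder to answer.

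**Working it through.** The plan has no figure to reproduce. The sample size of up to 30 is given without an effect size or SD for insulin sensitivity.

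**Inputs from the documents:** the meal (110 g carbohydrate), sampling at 0, 30, 60, 120 and 180 minutes, n = 30, a paired test, and two-sided alpha 0.05.

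**Assumed inputs:** the standard form of the index, the reductions g and i below, the simulation parameters, and the SDs.

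**1. Arithmetic.** The standard form is M = 10000/√(G0 × I0 × Gmean × Imean), where G0 and I0 are fasting values. Hold these fixed, and let mean glucose fall by a fraction g and mean insulin by a fraction i. The ratio of the new index to the old is then 1/√((1−g)(1−i)).
- g = 5%, i = 15%: 1/√(0.95 × 0.85) = 1.113, a rise of 11.3%.
- g = 10%, i = 30%: 1/√(0.90 × 0.70) = 1.260, a rise of 26.0%.
- g = 0, i = 10% or 20%: rises of 5.4% and 11.8%.

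**2. Does slower absorption lower the means at all?** Lower peaks do not settle this, because absorption is also later. A minimal-model simulation of the 110 g meal held insulin sensitivity fixed and varied only absorption.
- In one setting, with a time constant of 35 minutes, glucose was 108, 228, 294, 165, 116 (mean 182.2) and insulin 12, 47, 98, 52, 19 (mean 45.6).
- With 65 minutes, glucose was 108, 153, 210, 194, 153 (mean 163.6) and insulin 12, 25, 54, 60, 38 (mean 37.8).
- The index ratio is √((182.2 × 45.6)/(163.6 × 37.8)) = 1.159, or 16.1% before rounding the values.

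With full absorption, time constants of 50 to 100 minutes gave rises of 6.0% to 36.4%. This covers two insulin-secretion settings and both arithmetic and AUC means. Including runs with 10% less carbohydrate absorbed, the range was about 5% to 42%. Fasting glucose and insulin were fixed in this model, so a fasting index did not change, by construction.

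**3. Could the paired test detect it?** Noncentral-t power on the log index, n = 30, for assumed SDs of the log difference:

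| Rise from absorption alone | SD 0.2 | SD 0.3 | SD 0.4 |
|---|---|---|---|
| 10% | 0.71 | 0.39 | 0.24 |
| 18% | 0.99 | 0.83 | 0.59 |

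**4. The part that may be real.** The Background expects acarbose to lower fasting insulin. If fasting insulin fell by 10% (assumed) with the means unchanged, the fasting term alone would raise the index by 1/√0.90 − 1 = 5.4%. A fasting index would show that part.

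**5. Sampling times.** With samples at 0, 30, 60, 120 and 180 minutes, three of five (60%) fall in the first hour. Sampling every 30 minutes to 180 minutes (end time assumed) gives three of seven (43%). A simple mean weights the early rise differently under the two schedules.

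**The case against.** A reader might infer that the trial will report a false improvement in insulin sensitivity. The documents do not support that. The mechanism needs drug to be acting during the meal, and no section says that it is. The dosing instruction points that way and nothing suspends it, but Visit 4 takes place as the treatment period is completed and unused medication is returned there. The text sets a morning time only for the screening OGTT; a morning test meal is inferred from the overnight fast. Without a dose at that meal the mechanism is largely absent, and a change in the index could be real. The undefined modification might also behave differently from the standard form. These objections stand, and they make the point conditional.

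A reader might also infer that a fasting index should replace the meal index. The plan gives reasons for the meal test, namely physiological relevance and capture of the incretin contribution. A fasting index mainly reflects hepatic sensitivity, while the biopsied tissues are muscle and fat. The case for replacement therefore fails, but the case for adding a fasting index does not.

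Finally, the outcome is secondary in an exploratory study, C.3.2 already warns that phenotype associations will be complex, and no data would be lost. This limits the consequence. It does not answer the labelling problem, since the planned AUCs are post-meal measures too.

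**Conclusion.** The point holds conditionally. If study drug is acting during the test meal, which the dosing instruction makes likely, slower absorption alone could raise the only named insulin-sensitivity measure. Under the standard formula with fasting values fixed, the rise is about 11-26% for the assumed reductions of 5-10% in mean glucose and 15-30% in mean insulin. At n = 30, even a 10% rise could reach significance with probability 0.24 to 0.71 over the assumed SDs. None of the reductions, SDs or model parameters comes from the documents.

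It does not follow that every rise would be an artefact, because lower fasting insulin is expected and enters the index. Nor does it follow that the main aim is compromised: the acarbose-placebo differential-expression analysis does not use this index. What is affected is the paired insulin-sensitivity test and the Sub-aim 1 correlations that use it.

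**What to change.** - **Add a fasting index.** In C.2.2 and C.3.2, pre-specify one from the fasting glucose and insulin already drawn at visits 4 and 6, for example HOMA-IR or 1/(fasting glucose × fasting insulin). Report it beside the modified Matsuda index in the paired tests and the Sub-aim 1 correlations.
- **Limit the claim.** State that a rise in the meal-based index without a matching change in the fasting index will be reported as a post-meal response on treatment, not as improved insulin sensitivity. Say in advance what counts as matching. HOMA-IR falls when sensitivity improves.
- **Define the modified index**, with its formula and the samples that enter the means.
- **State and record whether study drug was taken with the test meal**, handled the same way at visits 4 and 6. This review takes no position on which it should be.
- **Reconcile the two sampling schedules** in the C.1 footnote and C.2.2.

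The cost is some wording, one extra derived variable and one recorded item, with no new samples for the fasting index. The downside is that a fasting index mainly reflects hepatic sensitivity, so it supplements the meal index and does not replace it. A real gain in peripheral sensitivity seen only after the meal would be described cautiously.

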Study Title: Study of Acarbose in Longevity

NCT02953093

IRB Number: 2016-6933

IRB Approval Date: 10/05/2018

Study of Acarbose in Longevity (SAIL)

A. Introduction and Specific Aims:

Acarbose, an FDA approved drug for the treatment of type 2 diabetes, has known effects on glucose metabolism. Evidence from mice indicates that acarbose may prolong lifespan. In humans, acarbose improves inflammatory markers and reduces cardiovascular events. Consequently, acarbose is of interest in clinical translational aging research since it may influence fundamental processes that contribute to age-related diseases. We herein propose an exploratory study to examine the effect of acarbose treatment on the biology of aging in humans. Specifically, we plan to investigate whether treatment with acarbose will restore the gene expression profile of older adults to that of young healthy subjects.

Specific Aims: We propose a 5 month randomized, double blind, placebo-controlled, cross-over study of acarbose treatment in older men (age > 60, n=30), with the following aims:

Specific Aim 1: To assess the effect of acarbose on gene expression profile, with a focus on molecular pathways known or suspected to play a role in aging.

Sub-aim 1: As a secondary analysis, we plan to assess the relationship between changes in gene expression with selected phenotypic variables and biomarkers, including changes in insulin sensitivity and glucose tolerance, vascular function, oxidative stress, inflammation, gut bacteria and/or serum microRNA profiles.

Specific Aim 2: To determine if treatment with acarbose will restore the gene expression profile of older, glucose intolerant men to that of young, healthy subjects.

B. Background and Significance:

Aging is a well-established risk factor for many disabling diseases including diabetes, cardiovascular disease, Alzheimer's disease and cancer. In fact, the risk of death from these causes is dramatically accelerated (100-1000 fold) between the ages of 35 and 85 years. There has been growing interest in understanding common pathways that accelerate age-related diseases, with the goal of therapeutically targeting such pathways to maintain health in older age. Several agents increase lifespan and prevent diseases of aging in animals, but studies in humans are needed.

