Muscle and adipose are key metabolic tissues that undergo significant age-related changes, and play an active role in the pathogenesis of aging. ²⁷⁻²⁹ We are characterizing transcriptional changes with aging in these tissues, and studying the effects of therapeutic interventions. RNA-Seq analysis is being used to identify pathways targeted by candidate anti-aging drugs that have been tested in animals. In addition, we are accumulating a repository of muscle and adipose biopsy samples obtained from young healthy controls to establish a unique biological "fingerprint" for aging in these tissues by comparing changes in gene expression in older adults, post-drug therapy to the profiles of young healthy subjects. This overall approach is supported by a grant from the Glenn Foundation for the Study of the Biology of Human Aging and we are currently analyzing data from two prior studies using metformin and resveratrol. We have gene transcription profiles from RNA seq performed on fat and muscle biopsies from 4 young individuals and plan to recruit up to 30 more young participants under a separate protocol.

As part of our secondary analyses, we also plan to assess changes in microRNA levels in the serum. MicroRNAs (miRNAs) are small, non-coding RNAs that regulate gene expression at a post-transcriptional level. Due to their stability in blood, changes in expression of circulating miRNA might serve as markers for age-related pathologies. Investigators at Einstein have profiled B-lymphocyte miRNA levels in the plasma and have identified microRNA profiles associated with exceptional longevity. We hypothesize that acarbose treatment will alter the expression of circulating miRNAs in a way that may offer insight into anti-aging mechanisms of acarbose. Given the known effects of acarbose on colonic fermentation and composition of gut microbiota we plan to explore changes in gut microbiome using 16s rDNA seq. We plan to correlate changes in transcription (muscle and fat RNAseq), post-translational regulation (miRNA) and gut microbiome with changes in clinical metabolic outcomes and inflammatory biomarkers.

C. Research Methods:

C.1. Study Design & Protocol Summary: We propose a 22-week randomized, double-blind, placebo controlled cross-over study of acarbose in older adults (n=30) with impaired glucose tolerance.

		Treat-			Wash	Treat-		
		ment A			-out	ment b		
	Visit 1	Visit 2 0	Visit 3 4 wks	Visit 4 10 wks	2 wks	Phone call: 12wks	Visit 5 16 wks	Visit 6 22 wks

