Men; age >60 years with IFG or IGT based on 75g OGTT (fasting plasma glucose 100 - 125 mg/dl and/or 2-hr glucose between 140 - 199 mg/dl,), or mild untreated diabetes based on OGTT (fasting plasma glucose 126 - 139 mg/dL and/ or 2 hr glucose between 200 - 249, with a hemoglobin A1c <6.5). We chose these inclusion criteria in order to study subjects who have evidence of impaired glucose regulation, but do not meet criteria for pharmacologic treatment of diabetes.

Exclusion:

1. Serious chronic or acute illness: cancer, clinically significant congestive heart failure, COPD, inflammatory conditions, eGFR<45, active liver disease, poorly controlled hypertension, epilepsy, recent (within 3 months) CVD event (MI, PTCA, CABG, stroke), inflammatory bowel disease; history of bariatric or other gastric surgery, cigarette smoking, serious substance abuse.

- 3. Hypersensitivity to acarbose or any component of the formulation
- 4. Patients taking anti-coagulant medications (e.g., warfarin) or anti-platelet drugs are excluded because of the increased risk of bleeding from muscle and fat biopsies. People taking aspirin for primary prevention who can safely stop the medication for 7 days may be included.
- **C.1.4. Acarbose dose and formulation:** Studies have demonstrated the ability of acarbose to delay or prevent the onset of diabetes in people with impaired glucose intolerance or pre-diabetes. The usual therapeutic dose ranges from 150 mg to 300 mg a day. For this study, we plan to use the maximum tolerated dose of up to 300 mg daily of acarbose. The drug will be introduced at 25mg daily, to be taken with the first bite of a meal. This will be increased to 25mg three times daily, then doubled in 1-2 weeks to 50mg 3 times daily as tolerated, and further doubled in another 1-2 weeks to 100mg 3 times daily as tolerated. Participants may continue to actively participate in the study with a reduced, but tolerable, dose of acarbose (minimum 75 mg daily). Capsules that contain 25mg acarbose or a similar appearing placebo containing lactose will be prepared by the Weiler Hospital research pharmacy.
- **C.1.5. Duration of treatment:** We propose 2x 10-week duration of treatment (4 weeks titration, 6 weeks maximal dose) with a 2-week washout between treatment periods. We have reasoned that this time frame should be sufficient to see effects on gene expression.

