C.2.3 Specific Aim 2: To determine if treatment with acarbose will restore the gene expression profile of older, glucose intolerant men to that of young, healthy subjects. We hypothesize that transcriptional changes detected above may reflect some aspects of the transcription profiles of younger adults and provide insight into specific pathways affected by acarbose.

Under a separate protocol (2016-7110), young individuals aged 20-40 will be recruited and will undergo fat and muscle biopsies for RNA sequencing as detailed above. Changes

seen in the acarbose group in muscle and fat transcriptome will be compared to the young transcriptome, to identify aging-specific pathways affected by acarbose

C.3. Data analysis, rationale, limitations of experimental design:

C.3.1 Study design: We plan to conduct a double-blind placebo controlled trial with crossover design. The previous studies performed by our group (resveratrol and metformin) were cross-over studies with gene transcription data on 16 and 14 individuals, respectively. We identified clear differences in gene transcription profiles between resveratrol and placebo, using the same criteria outlined above. We expect that acarbose would have a similar if not larger effect size, thus 30 individuals in a crossover design is sufficient to detect differences. Data are still being analyzed for the metformin study. Cross-over study design is advantageous in terms of increased power for the study size. However, there is a risk for carryover effects since metabolic, transcriptional, and gut microbial changes may persist after the medication is cleared from circulation during the 2-week washout. Therefore, we plan to also separately analyze those who received treatment first in a sub-analysis to detect any long lasting changes that may result in a carry-over effect. Changes in physical activity and diet could confound interpretation of our metabolic studies, although the double-blind, placebo controlled study design will help to mitigate any potential impact. Changes in weight and body composition will also be carefully monitored. If there are significant changes in physical activity or weight, we will adjust for these in our data analysis.

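### Aim 2 compares older men selected for impaired glucose regulation with young healthy subjects, so the contrast cannot support a conclusion about 'aging-specific' pathways

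*Combined protocol and SAP*

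**What the plan says.** Aim 2 asks whether acarbose will "restore the gene expression profile of older, glucose intolerant men to that of young, healthy subjects". Section C.2.3 draws the inference: changes "seen in the acarbose group in muscle and fat transcriptome will be compared to the young transcriptome, to identify aging-specific pathways affected by acarbose".

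The older group is defined in C.1.2: "Men; age >60 years with IFG or IGT based on 75g OGTT", or mild untreated diabetes on the same test. The selection is deliberate, in order to "study subjects who have evidence of impaired glucose regulation, but do not meet criteria for pharmacologic treatment of diabetes".

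The comparators come from outside the trial: "Under a separate protocol (2016-7110), young individuals aged 20-40 will be recruited". Section B reports "biopsies from 4 young individuals and plan to recruit up to 30 more young participants under a separate protocol". It describes the ageing 'fingerprint' as obtained by "comparing changes in gene expression in older adults, post-drug therapy to the profiles of young healthy subjects". This document characterises the young group only by age and as healthy.

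Section C.3.2 plans negative binomial contrasts of young with old and of acarbose with placebo, and names no glycaemic covariate or stratum. The limitations in C.3.1 cover carryover, diet, physical activity and weight. Sub-aim 1 (C.2.2) relates expression changes to changes in insulin sensitivity and glucose tolerance, among other variables.

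**The concern.** The young-old difference contains whatever age does to expression plus whatever dysglycaemia does. No older normoglycaemic sample and no young dysglycaemic sample is described, so nothing in the planned comparison separates the two. Section B states that acarbose lowers blood glucose. A gene that differs from the young only because the older men are dysglycaemic, and that shifts under acarbose, would fit the description in C.2.3 of an ageing-specific pathway affected by the drug.

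What is at stake is the interpretation of Aim 2. Restoration of a younger profile could not be distinguished from partial correction of impaired glucose regulation. C.3.2 intends the results to inform later, targeted studies, so a mislabelled pathway would be carried forward.

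**Working it through.** The plan attaches no figure to the young-old comparison, so there is none to reproduce. The question is what the design can identify.

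**Step 1: the groups (C.1.2, C.2.3).**

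| | No dysglycaemia | Dysglycaemia |
|---|---|---|
| Young, 20-40 | comparators, described as healthy | none described |
| Older men, >60 | cannot enter | all trial participants |

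**Step 2: identifiability.** Write mean expression of a gene as b0 + bA·A + bD·D, with A = 1 for older and D = 1 for dysglycaemic. The planned groups give the design rows (1,0,0) and (1,1,1), which have rank 2 for 3 parameters. The young-old contrast estimates bA + bD only. Adding older normoglycaemic men would add the row (1,1,0) and raise the rank to 3. More participants of the two existing kinds would not. Nor does it matter which biopsy of the older men serves as 'old', since all come from the same selected men.

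**Step 3: two genes that look the same.** Let acarbose reverse a fraction f of a gene's difference from the young.
- Gene 1: bA = 0, bD = d. The difference is d, and falls to (1 − f)d under acarbose.
- Gene 2: bA = d, bD = 0. The difference is d, and falls to (1 − f)d under acarbose.

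The Aim 2 comparison gives the same result for both.

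**Step 4: a simulation of the mechanism, not of its size.** All inputs are assumed except the group sizes: 30 older men, and 4 or 4 + 30 = 34 young. The gene has no age effect, unit SD and within-person correlation 0.5. It is flagged if post-placebo expression differs from the young and acarbose moves it back, each at unadjusted p < 0.05. With a dysglycaemia effect of 1 SD, half of it reversed, the gene is flagged in 36% of runs with 4 young and 74% with 34. Over effects of 0.5 to 1.5 SD and reversals of 25% to 75%, the range is 2% to 78% with 4 young and 8% to over 99% with 34. With no effect at all and 34 young it is 0.6%. A larger young group therefore raises the flag rate. C.3.2 uses adjusted p-values and a fold change above 2 for acarbose against placebo, so these rates do not describe the planned filter.

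**Step 5: can associations within the older men do the separating?** For a correlation r, power ≈ Φ(atanh(r)·√(n − 3) − z), where z is the two-sided critical value. With n = 30, √27 = 5.196. The values of r and the stricter alpha are assumed.

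| r | atanh(r) × 5.196 | alpha 0.05 (z = 1.960) | alpha 0.001 (z = 3.291) |
|---|---|---|---|
| 0.3 | 0.3095 × 5.196 = 1.608 | Φ(−0.352) = 36% | Φ(−1.683) = 5% |
| 0.5 | 0.5493 × 5.196 = 2.854 | Φ(0.894) = 81% | Φ(−0.437) = 33% |

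So 19% to 64% of truly glycaemia-related genes would be missed at 0.05, and 67% to 95% at 0.001. A list of genes with no detected association would still contain many of them.

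**The case against.** The strongest reply is that the plan is open about its population and modest in its claims. The title of Aim 2 names glucose-intolerant men, the hypothesis in C.2.3 is hedged, and C.3.2 calls the analyses exploratory and associations with phenotypes complex. Sub-aim 1 already plans to relate expression changes to changes in glucose tolerance, and C.2.2 provides glucose and insulin AUC. All of this stands and limits the consequence. It does not rescue the term 'aging-specific'. Sub-aim 1 can show which acarbose effects track glycaemic change, but it cannot say why older and young differ, and nothing ties it to the Aim 2 gene list.

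Two further points are fair. The glycaemic criteria of the young are in a separate protocol not available here; whatever they are, young subjects cannot supply the missing older normoglycaemic group. Dysglycaemia may also be partly a result of ageing, so removing every glycaemia-related gene could over-adjust. That argues against filtering. It does not justify the ageing label, because here dysglycaemia was made universal by selection.

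A reader might go further and infer that the error favours the hypothesis because acarbose moves mainly glucose-responsive genes, or that most 'restored' genes would be dysglycaemia genes. The documents support neither. Section B reports longer mouse lifespan with unchanged HbA1c and lists gut microbiota, butyrate, gut hormones and absorbed metabolites as possible routes. Biopsies are taken fasting (C.2.1), while the described glucose effect is mainly postprandial. Nor is acarbose given here to treat glucose: Section B presents it as a candidate anti-ageing agent, with glucose lowering as its pharmacology.

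**Conclusion.** The point holds as one of identifiability. With the two groups described, age and dysglycaemia are fully aliased as group factors (rank 2 of 3), and the contrast in C.2.3 cannot support a conclusion about ageing-specific pathways. This rests only on the eligibility criteria, the description of the comparators and the absence of any glycaemic term in the young-old model. The number of genes affected cannot be estimated from the documents.

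It should not be read as a flaw in the trial as a whole. The randomised acarbose-placebo comparison of Aim 1 is untouched, and the choice of population is not at issue. Only the ageing attribution in Aim 2, and the related statements in Section B and C.3.2, go beyond what the design can show.

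**What to change.** 1. **Wording.** In C.2.3, replace 'aging-specific' with 'differing between older men with impaired glucose regulation and young healthy subjects'. Make the matching change where C.3.2 refers to transcript changes with ageing and Section B to an ageing fingerprint. Add the confounding of age with dysglycaemia to the limitations in C.3.1.

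2. **Link Sub-aim 1 to Aim 2.** For each gene reported as moved toward the young profile, report descriptively (a) its association with post-placebo HbA1c and meal-test glucose, and (b) whether its acarbose-placebo change tracks the same man's change in glucose AUC. HbA1c and the meal test are scheduled at both biopsy visits (C.1 schedule, visits 4 and 6).

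3. **Limit its use.** State that this is annotation only. With up to 30 men, lack of association is not evidence of an ageing effect, and no ageing claim should rest on a list of genes labelled unrelated to glycaemia.

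The cost is revised text and a little extra analysis of data already planned, with no new participants or samples. The price is a more qualified ageing claim.
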